Aim 1 (Phase 1): Estimate the differential brain fMRI response between XRNTX and XRBUP in OUD treatment groups. We hypothesize that (**H1**) XRBUP and XRNTX will modulate the regional brain activity in the two-key cognitive-behavioral domains and measures of brain connectivity from pre-treatment (PRE) to on-treatment (ON) and this response will differ between the two medications. Milestone for transition to Phase 2: The MAT group (XRNTX, XRBUP) by Session (PRE, ON) **interaction** will have at least small ($d' \geq 0.2$) effect size in all brain measures.

H1a: Incentive salience (opioid cue-reactivity task): The decrease in the brain response to drug related stimuli (ON minus PRE) in the medial prefrontal cortex (mPFC) and the ventral striatum (VS) will be **greater** in the XRNTX than in the XRBUP group.

H1b: Executive function (Go-NoGo task): XRNTX will improve the efficiency of response inhibition more than XRBUP, leading to a greater **decrease** in the brain signal (ON vs PRE) during the NoGo trials in the inferior frontal cortex in the XRNTX group (see A.2.b).

H1c: Resting state functional connectivity (rsFC): change (ON vs PRE) in the rsFC between the VS and the right inferior frontal gyrus (rtIFG) and the mPFC will be **greater** in the XRNTX (vs. XRBUP group).

Aim 2 (Phase 2): Confirm in the full sample (n=200), the significance of MAT (XRNTX, XRBUP) by Session (PRE, ON) interaction in all domains from Aim 1. Test the explanatory value of integrated brain-behavior models of relapse vulnerability, identify differences in variable loading between MAT group, and explore potential mechanism of individual variability in treatment outcome.

H2a: Using logistic regression, we will test the explanatory value of brain signal in modeling treatment failure (Section **C.5.c**) and identify specific variables that differentiate MAT groups (interaction).

H2b (Exploratory): Test if the models that include brain response better explain treatment success or failure when compared to those fitted solely with demographic and clinical measures: demographic + clinical measures vs. demographic + clinical measures + brain response).

3.3 Secondary Study Endpoints (abbreviations spelled out on Page 27, “STUDY MEASURES”):

Depression (HAM-D2); Anxiety (HAM-A); Opioid Withdrawal (COWS); Opioid Craving (Opioid Craving Scale); TLFB interview; Percent UDS positive for cocaine (Ten-drug urine screen)

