9 STATISTICAL CONSIDERATIONS

9.1 Statistical Hypotheses

Overview of primary hypotheses: Our primary response will be a binary indicator of treatment failure on the XRNTX or XRBUP regimen, defined as ≥ 2 weekly UDS positive for opioids, or self-report of ≥ 2 periods of three or more days of opioid use, or refusing XRNTX or XRBUP, or dropping out of study entirely. In hypotheses H1a and H1b, we are examining the effects of small, pre-specified, sets of measures, so our analyses will focus on model fit and prediction, and not on model selection. In hypothesis H1c, we search for best sets of predictors among demographic and clinical-behavioral variables, and over sets of brain/neural measures, so our focus is on model selection and on avoiding overfitting to the available data.

R61 Phase:

Hypothesis H1 (fMRI): For each of the cue reactivity (H1a), response inhibition (H1b), and connectivity (H1c) brain measured, we have a small number of neural responses associated with one or two regions of interest. These variables are continuously distributed, so we will test Hypotheses 1a, 1b and 1c using a repeated measures analysis of variance (rm-anova). The models will include a within-subject factor for Session (PRE vs ON) and a between-subject factor Group (XRNTX vs XRBUP), and their interaction. To accommodate the anticipated non-normal distributions of the response, we will use a generalized estimating equation (GEE) approach, using robust standard errors, using a compound symmetry working correlation structure for the within-subject correlations between the PRE and ON fMRI scans (Diggle PJ et al 2002). We will perform the rm-anova separately for each ROI (mPFC and VS for H1a, IFC for H1b, and VS-rtIFG and VS-mPFC for H1c). The hypotheses will be addressed by the Session by Group interaction, and we will obtain estimates and standard errors of the PRE vs ON change within each of the two groups, along with the size, standard error and significance of the differences between these estimates.

Sample size considerations for sample: The sample size is adequate for application of the GEE methods to obtain robust standard error (Lipsitz et al 1994). For a test of the PRE vs ON effect, our sample yields 80% power for a one-sided test that the ON levels will be Cohen's $d=0.4$ lower than the PRE levels, consistent with a decrease of Cohen's $d=0.5$ observed in our preliminary data and a decrease of Cohen's $d=0.3$ in the Suboxone sample.

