Milestone for transition from Phase 1 to Phase 2: Using the models described above, we will obtain (model-based) estimates of the Session (PRE vs ON) by Group (XRNTX vs XRBUP) effects for the five hypotheses described above. If these estimates show at least small effects (Cohen's $d \geq 0.2$) in at least two of the three domains, then we will continue to the R33 phase.

Primary Analyses for Phase 2: Session by Group interaction effects on neural response: First, we will formally test the interaction effects explored in the R61 phase. We will rerun the analyses described for H1a, H1b and H1c in the R61 phase, for the full sample of $n=140$ obtained through the R61 and R33 phases. The models will be exactly as described in the R61 phase.

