Effects of neural response on relapse vulnerability: Our primary outcome combines adherence to treatment and frequency of illicit opioid use during treatment. The primary outcome is a binary indicator of treatment success: if a patient provides ≥ 2 weekly UDS positive for opioids, or self-report of \geq two or more periods of ≥ 3 days of opioid use, or refuses XRNTX or XRBUP, or drops out of treatment entirely, then they will be classified as a treatment failure; otherwise they will be classified as a treatment success. We will calculate the PRE-ON change in %-signal-change for each of the regions and neural responses described in the R61 phase. We will use logistic regression models to predict the log-odds of treatment success (Aitkin et al 2009). The predictors in the model will be a binary factor for Group (XRNTX vs. XRBUP), and the neural change scores. We anticipate that there will be some greater PRE to ON changes in the XRNTX group than in the XRBUP group, so there will be some confounding between the effects of change score and the effects of Group on the rates of positive UDS. Thus, we will include Group first in our model, so evaluating the Group effect separate from the change-score effects, and then include the change scores in a model including Group, so evaluating the additional effect of change-scores in addition to the existing effects of Group. To assess whether the effects of the change scores differ between the XRNTX and XRBUP groups, we will also test for interaction effects between Group and each of the change-scores, by adding the interaction terms to the model that includes the group and neural change score main effects. We will check the assumptions underlying the logistic regression models (e.g. linearity of covariates effects on log-odds, outliers, influential observations) using standardized residuals, influence diagnostics, and graphical displays.

Sample size considerations for the sample: Analyses of Session by Group effects on neural response: For a one-sided test that the PRE vs ON effect is larger in the XRNTX group than in the XRBUP group, our sample of 70 per group yields 81% power for an effect of $d=0.42$ or greater. This effect is similar to the effects observed in the preliminary data. On the basis of the preliminary data we anticipate Group by Session effects of approximately $d=0.38$ in the VS and $d=0.42$ in the mOFC.

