
9.2 Sample Size Determination:

Analyses of Session by Group effects on neural response: For a one-sided test that the PRE vs ON effect is larger in the XRNTX group than in the XRBUP group, our sample of 80 per group yields 81% power for an effect of $d=0.42$ or greater. This effect is similar to the effects observed in the preliminary data. On the basis of the preliminary analysis, we anticipate Group by Session effects of approximately $d=0.38$ in the VS and $d=0.42$ in the mOFC.

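### The confirmatory power is for a one-sided test, but the analysis text fixes no tail or alpha and H1c has no sign; if the interaction is tested two-sided at 5%, power is about 69% or 75%

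*Combined protocol and SAP*

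**What the plan says.** **Power.** Section 9.1 (Phase 2 sample size) and Section 9.2 use the same one-sided basis: "For a one-sided test that the PRE vs ON effect is larger in the XRNTX group than in the XRBUP group". Section 9.1 continues "our sample of 70 per group yields 81% power for an effect of $d=0.42$ or greater"; Section 9.2 continues "our sample of 80 per group yields 81% power for an effect of $d=0.42$ or greater". Both expect similar effects: "we anticipate Group by Session effects of approximately $d=0.38$ in the VS and $d=0.42$ in the mOFC".

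**Hypotheses.** The umbrella H1 (Section 3.2, repeated in 9.4.1) says the two drugs will change brain activity "and this response will differ between the two medications", and the synopsis likewise treats the interaction as the sign of a difference between them. The sub-hypotheses are more specific:
- H1a predicts a larger decrease with XRNTX in mPFC and VS.
- H1b predicts a larger decrease with XRNTX in the inferior frontal cortex.
- H1c says the "change (ON vs PRE) in the rsFC between the VS and the right inferior frontal gyrus (rtIFG) and the mPFC will be" greater in XRNTX than in XRBUP. It does not say whether connectivity is expected to rise or fall.

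**Analysis.** Section 9.1 specifies a repeated-measures model fitted by GEE for each region: "The hypotheses will be addressed by the Session by Group interaction". It promises the change in each group, and the size, standard error and significance of the difference. Phase 2 reruns the same models "for the full sample of $n=140$ obtained through the R61 and R33 phases". No alpha or tail is given for these tests. The alphas of 0.05 and 0.025 in Section 9.1 belong to the logistic regression power.

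**The concern.** A power figure is useful only if it belongs to the test that will be run. Here the tail appears only in the sample-size text. The question is worded as a difference, and the analysis is an interaction reported for significance, which most analysts would run two-sided by default. If they do, the power is about ten points lower than a one-sided calculation gives, and the claim in Section 10.2 that power for the primary hypotheses is ample becomes hard to sustain.

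The second problem concerns H1c. For H1a and H1b the group order and the sign of the change together fix the rejection tail. For H1c, a greater change with XRNTX could mean a larger rise or a larger fall in connectivity, and these lie in opposite tails. The plan does not say which tail counts as confirmation for VS-rtIFG and VS-mPFC, so that choice is left to the analyst.

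**Working it through.** **Inputs from the plan**
- d = 0.42 (effect in the power statements, and expected in mOFC); d = 0.38 (expected in VS).
- n = 70 per arm (Section 9.1, from n = 140) or 80 per arm (Section 9.2).
- Stated power 81%, one-sided.

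**Assumptions, because the plan is silent for this test**
- Alpha = 0.05.
- d is the between-group difference in PRE-to-ON change, divided by the SD of the change.
- Equal allocation.

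**Formula.** With two sessions and two groups the interaction is a single contrast, a two-sample comparison of change scores. Power comes from the noncentral t with df = 2n − 2 and noncentrality d × √(n/2). The critical value is the 95th percentile of t (one-sided) or the 97.5th (two-sided).

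**Step 1: the plan's own figure (one-sided 5%, d = 0.42)**
- n = 70: noncentrality 0.42 × √35 = 2.485, df 138, critical value 1.656; power 79.6% (normal approximation 80.0%).
- n = 80: noncentrality 0.42 × √40 = 2.656, df 158, critical value 1.655; power 84.1% (normal 84.4%).

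The stated 81% is therefore close to the one-sided value at 70 per arm and about three points below it at 80 per arm. One-sided power of 81% at d = 0.42 corresponds to 73 per arm.

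**Step 2: the same contrast two-sided at 5%** (critical values 1.977 and 1.975)

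| n per arm | d | One-sided 5% | Two-sided 5% |
|---|---|---|---|
| 70 | 0.42 | 79.6% | 69.4% |
| 80 | 0.42 | 84.1% | 75.2% |
| 70 | 0.38 | 72.3% | 60.7% |
| 80 | 0.38 | 77.3% | 66.6% |

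At d = 0.42 the like-for-like loss is 79.6 − 69.4 = 10.2 points at 70 per arm and 84.1 − 75.2 = 8.9 points at 80 per arm. The effect detectable with 81% two-sided power is d = 0.483 (70 per arm) or 0.451 (80 per arm).

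**Step 3: range over the unstated alpha.** One-sided 2.5% gives the same values as two-sided 5%. Two-sided 2.5% gives 58.7% (70 per arm) and 65.3% (80 per arm) at d = 0.42. Of the levels tried (5%, 2.5% and 1%, each one- and two-sided), only one-sided 5% comes near 81% at 70 per arm.

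**Step 4: the H1c tail.** Under no difference, a one-sided 5% test rejects 5% of the time in its chosen tail. If the tail is chosen to match the observed sign, either tail can lead to rejection, so the error rate is 5% + 5% = 10%.

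**The case against.** The strongest reply is that the plan does state a tail, twice, and that it is one-sided; one of those statements sits in Section 9.1 beside the analysis it describes. A single-contrast interaction can legitimately be tested one-sided. Three of the five contrasts (mPFC, VS and inferior frontal cortex) have both group order and sign fixed in advance, in agreement with that basis. H1c also gives the group order. All of this stands.

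Three stronger readings are therefore tempting but unsupported.
- A reader might infer that the plan specifies a two-sided test, so that 69% to 75% is the true power of the test described. No section says two-sided; those figures hold only if the test is run that way.
- A reader might infer that H1c has no direction at all. It gives the group order; only the sign of the change is missing.
- A reader might infer that a larger XRBUP effect could not be reported. Section 9.1 commits to estimates and standard errors in each group and for their difference, so such an effect would be estimated. Only a formal rejection in that direction would be lost.

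Nor does the plan propose choosing the H1c tail after seeing the data. The 10% figure shows what the gap would allow, not what is intended.

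The reply does not supply a tail or alpha in the analysis text, reconcile the one-sided basis with a question about difference, or make a one-sided H1c test executable.

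**Conclusion.** The point holds as a gap in specification with a material effect on the stated power. The sample-size text assumes a one-sided test, the analysis text names neither tail nor alpha, and two of the five primary contrasts lack the sign that a one-sided test needs.

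The 81% is not the power of a two-sided 5% interaction test at either sample size: that power is 69.4% or 75.2% at d = 0.42, and 60.7% or 66.6% at the expected VS effect. If the one-sided 5% test is intended, 81% is about right for 70 per arm and too low for 80 per arm. Quoting one figure for both sizes is a separate inconsistency.

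These values rest on alpha 0.05, equal arms and d on the SD-of-change scale, and allow for no multiplicity adjustment across the five contrasts.

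**What to change.** State the tail and alpha for the five Group by Session tests in Sections 9.1 and 9.4, before any on-treatment data are analysed, and choose one of two routes.

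1. **Two-sided at 5%**, which matches the question of whether the drugs differ. In 9.1 and 9.2 restate power at d = 0.42 as about 69% (70 per arm) or 75% (80 per arm), or give the effect detectable with 81% power as d = 0.483 or 0.451.
2. **One-sided**, if that is intended. Say so in the analysis text with its alpha and state the expected sign of the H1c change in advance. At 5%, restate power as about 80% (70 per arm) or 84% (80 per arm). Acknowledge that a larger XRBUP effect could be estimated but not declared significant.

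Either way, use one sample size per arm throughout and add the power at d = 0.38. The cost is a few lines of text and, on the first route, a less favourable stated power. No extra patients are required.

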3.1 General Design

Study Design: The proposed study is a prospective open label 2-group study to compare the brain and behavioral responses of individuals with OUD receiving XRBUP and XRNTX treatments. The study will be conducted in two phases – Phase 1 = feasibility and Phase 2 = confirmation. Study interventions (XRNTX and XRBUP) and their duration will be same in both phases. Phase 1 (2 years) will have more cognitive and behavioral probes, some of which may not survive into Phase 2 (3 years) if found to not yield significant discrimination between the study interventions (groups). Participants will be men and women with current DSM-5 diagnoses of opioid use disorder (OUD) who will be randomized to XRBUP or XRNTX. Phase 1 will recruit 60 participants and Phase 2 will recruit 200 participants. The study length for each participant is comprised of up to 30 days of screening and baseline evaluations (called “week 1”), a 12-week open label trial (medication phase), and one follow-up visit 4 weeks after end of medication phase. The overall duration of the project will be 5 years (60 months). We intend to recruit 4 subjects per month for 40 months.

Table 1. Study timeline

Year/Phase	Year 1 (Phase 1)				Year 2 (Phase 1)				Year 3 (Phase 2)				Year 4 (Phase 2)				Year 5 (Phase 2)			
Quarter	Q1	Q2	Q3	Q4																
Preparation	X	X	X	X					X	X										
Recruitment		X	X	X	X	X	X	X	X	X	X	X	X	X	X	X	X			
Data Collection		X	X	X	X	X	X	X	X	X	X	X	X	X	X	X	X			
Data Analysis/QC			X	X	X	X	X	X	X	X	X	X	X	X	X	X	X	X	X	X
Publication				X	X			X	X			X	X			X	X	X	X	X

Figure 1: Outline of study interventions

3.2 Primary Study Endpoints (see Table in the Schedule of Activities (SoA), [Appendix Section 12.1](#)).

Clinical:

- 1) percent of the urine drug screen (UDS) tests positive for opioids during the last month of participation.
- 2) The number of study interventions (1,2 or 3) participant adhered to.

Surrogate: Brain fMRI response in three cognitive domains:

- 1) Response inhibition (Go-NoGo task)
- 2) Drug cue reactivity (Opioid Cues task)
- 3) Emotional identification (IDemo Task)
- 4)

Primary Hypothesis:

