5.3 Strategies for Recruitment and Retention

Recruitment: The project team has an established track record of recruiting for and conducting neuroimaging studies of OUD that include office-based detoxification and induction to XRNTX or XRBUP (Langleben et al 2014, Wang et al 2015, Shi et al 2018, Wang et al 2018). The team has established relationship with a network of addiction treatment facilities in the metro Philadelphia area, from which we have been recruiting participants with OUD for over a decade. This network includes two full-service academic opioid treatment programs as well as six community inpatient facilities and numerous office-based practices. The network guarantees access to a diverse and representative population spanning urban, suburban, and rural settings. Finally, our community and media outreach, (Bender 2013) as well as social media advertising, have been highly effective means of supplementing the clinical referrals of participants. From all these combined sources, we expect to recruit a total of 200 participants. Approximately 75% will achieve the opioid abstinence status to receive the 1st monthly XR MAT injection, to a total of 160 anticipated by the power analysis. We budget an additional 10% of scanner time to account for data loss due to motion artifacts and technical problems. Access is a challenge in health care and a research confound. Insufficient transportation could impose selection bias against individuals with lower SES, disabilities and history of impaired driving which are all overrepresented among individuals with OUD. We will address this issue by reimbursing for private or public transportation expenses and access to cost-effective prepaid car services and substituting some in-person visits by telephone and electronic communications.

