Primary Hypothesis: Estimate the differential brain fMRI response between XRNTX and XRBUP in OUD treatment groups. We hypothesize that **(H1)** XRBUP and XRNTX will modulate

the regional brain activity in the two-key cognitive-behavioral domains and measures of brain connectivity from pre-treatment (PRE) to on-treatment (ON) and this response will differ between the two medications. Milestone for transition to Phase 2: The MAT group (XRNTX, XRBUP) by Session (PRE, ON) **interaction** will have at least small ($d' \geq 0.2$) effect size in all brain measures.

H1a: Incentive salience (opioid cue-reactivity task): The decrease in the brain response to drug related stimuli (ON minus PRE) in the medial prefrontal cortex (mPFC) and the ventral striatum (VS) will be **greater** in the XRNTX than in the XRBUP group.

H1b: Executive function (Go-NoGo task): XRNTX will improve the efficiency of response inhibition more than XRBUP, leading to a greater **decrease** in the brain signal (ON vs PRE) during the NoGo trials in the inferior frontal cortex in the XRNTX group.

H1c: Resting state functional connectivity (rsFC): change (ON vs PRE) in the rsFC between the VS and the right inferior frontal gyrus (rlIFG) and the mPFC will be **greater** in the XRNTX (vs. XRBUP group).

Secondary Hypotheses: Confirm in the full sample (n=140), the significance of MAT (XRNTX, BUP-NTX) by Session (PRE, ON) interaction in all domains from Aim 1. Test the explanatory value of integrated brain-behavior models of relapse vulnerability, identify differences in variable loading between MAT group, and explore potential mechanism of individual variability in treatment outcome.

H2a: Using logistic regression, we will test the explanatory value of brain signal in modeling treatment failure and identify specific variables that differentiate MAT groups (interaction).

H2b (Exploratory): Test if the models that include brain response better explain treatment success or failure when compared to those fitted solely with demographic and clinical measures: demographic + clinical measures vs. demographic + clinical measures + brain response).

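### Sections 9.1 and 9.2 claim the same 81% power for 70 and for 80 per group, and no consistent participant flow leads from 200 recruits to the PRE/ON scan pairs the test needs

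*Combined protocol and SAP*

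**What the plan says.** The confirmatory analysis of Phase 2 is the Group (XRNTX, XRBUP) by Session (PRE, ON) interaction in the fMRI signal. Its sample size is described in several places.

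- Section 9.1, sample size considerations for Phase 2: "our sample of 70 per group yields 81% power for an effect of $d=0.42$ or greater".
- Section 9.2, for the same one-sided test: "our sample of 80 per group yields 81% power for an effect of $d=0.42$ or greater". Both sections expect about d=0.38 in the ventral striatum (VS) and d=0.42 in the mOFC.
- Section 9.1, primary analyses for Phase 2: the models are rerun "for the full sample of $n=140$ obtained through the R61 and R33 phases". Section 9.4.1 agrees: "Confirm in the full sample (n=140), the significance of MAT".
- Section 3.2, Aim 2: "Confirm in the full sample (n=200), the significance of MAT (XRNTX, XRBUP) by Session (PRE, ON) interaction in all domains from Aim 1".
- Section 5.3 expects 200 recruits and continues: "Approximately 75% will achieve the opioid abstinence status to receive the 1st monthly XR MAT injection, to a total of 160", and it ties that 160 to the power analysis. It adds: "We budget an additional 10% of scanner time to account for data loss due to motion artifacts and technical problems".
- Section 3.1: "We intend to recruit 4 subjects per month for 40 months".

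Section 9.3 defines the analysis population by receipt of at least one dose. The Schedule of Activities (13.1) puts injection 1 at day 10, injection 2 at day 40 and the ON scan at day 55. Section 4.1 notes high XRNTX drop-out in the first two months. Section 7.2 says that injected participants who later withdraw are not replaced.

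**The concern.** One test, at one effect size and one alpha, cannot have the same power at 70 and at 80 per group, so at least one of the two statements does not match its n. The totals do not settle which, because 140, 160 and 200 all appear as the sample for the same interaction, and the arithmetic meant to link 200 to 160 fails.

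The count also ends at the wrong event. An interaction on PRE-to-ON change is informed mainly by participants with both scans. The plan counts people at the first injection, 45 days before the ON scan, and never says whether 70 or 80 means injected participants or usable pairs.

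At stake is how a null result is read. If loss before day 55 is appreciable, or the VS effect is the anticipated 0.38, a non-significant interaction would be judged against more power than the test had.

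**Working it through.** **Inputs.** Per-group n of 70 (9.1) and 80 (9.2); d=0.42 and d=0.38 (9.1, 9.2); one-sided test (9.1, 9.2); 1:1 allocation, implied by the equal group sizes. Alpha is not stated for this test. I assume one-sided 5% and also show 2.5%. I take d as the between-group difference in PRE–ON change divided by the SD of that change.

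**Formula.** Two-sample t test, n pairs per group: noncentrality = d·√(n/2), df = 2n − 2. The normal approximation is power ≈ Φ(d·√(n/2) − 1.645).

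**Reproducing the stated 81% at d=0.42**

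- n=70: 0.42·√35 = 2.485; 2.485 − 1.645 = 0.840; power 80.0% (noncentral t 79.6%).
- n=80: 0.42·√40 = 2.656; 2.656 − 1.645 = 1.011; power 84.4% (noncentral t 84.1%).
- n for 81%: 2·[(1.645 + 0.878)/0.42]² = 72.2, so 73 per group.
- At one-sided 2.5%: 69.4% (n=70) and 75.2% (n=80).

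So 81% is close for 70 per group at one-sided 5%, and fits 80 per group at neither alpha.

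**Participant flow**

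- 200 × 0.75 = 150, or 75 per group, not 160. Reaching 160 needs 160/200 = 80%, or 160/0.75 = 213.3, so 214 recruits.
- 4 per month × 40 months = 160 recruits, not 200.
- Sample for the interaction: 140 (9.1, 9.4.1); 160 (2 × 80 in 9.2, and 5.3); 200 (Aim 2).

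**Power by number of usable pairs** (noncentral t, one-sided 5%)

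| Pairs per group | d=0.42 | d=0.38 |
|---|---|---|
| 60 | 74.0% | 66.4% |
| 65 | 76.9% | 69.5% |
| 70 | 79.6% | 72.3% |
| 73 | 81.1% | 73.9% |
| 75 | 82.0% | 74.9% |
| 80 | 84.1% | 77.3% |

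At d=0.38, 81% needs 2·[(1.645 + 0.878)/0.38]² = 88.1, so 89 pairs per group.

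**Loss before the day-55 scan.** The plan gives no rate, so these are scenarios. The 25% is the dropout rate section 9.1 states for the secondary substance-use outcomes, borrowed here as an assumption.

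| Injected per group | Loss | Pairs per group | d=0.42 | d=0.38 |
|---|---|---|---|---|
| 70 | 10% | 63 | 75.8% | 68.3% |
| 75 | 10% | 67.5 | 78.3% | 70.9% |
| 80 | 10% | 72 | 80.6% | 73.4% |
| 70 | 25% | 52.5 | 68.9% | 61.4% |
| 75 | 25% | 56.25 | 71.5% | 64.0% |
| 80 | 25% | 60 | 74.0% | 66.4% |

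Keeping 81% at d=0.42 requires 73/80 = 91% scan retention from 80 injected, or 73/75 = 97% from 75. It is not reached from 70.

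**If the GEE also uses PRE-only participants.** Under compound symmetry with equal SDs, the variance of the mean change per group, in units of the scan variance, is (1 − ρ²)/pairs + (1 − ρ)²/all. Dividing by 2(1 − ρ) puts it on the scale of the change. With 25% loss:

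- From 70: ρ=0 gives an effective n of 60 (74.0% at d=0.42, 66.4% at 0.38); ρ=0.5 gives 56 (71.4%, 63.8%).
- From 80: ρ=0 gives 68.6 (78.9%, 71.5%); ρ=0.5 gives 64 (76.4%, 68.9%).

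The extra PRE scans help, but do not restore 81%.

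**The case against.** Several points can fairly be made for the plan.

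- **70 per group is nearly right.** It gives 79.6% to 80.0%, and rounding in d could account for most of the gap. The likely error is that section 9.2 changed n without updating the power. This stands as the probable explanation, but it is an inference, and it leaves 9.2 wrong as written.
- **The 9.2 error is conservative.** With 80 usable pairs the power is 84%, so 81% understates it. True, but only if 80 means pairs.
- **The loss rate is assumed.** No document gives loss before day 55. The 25% belongs to other outcomes, and the 50% to 75% XRNTX retention in section 4.1 refers to the third injection, which is scheduled after the scan. Those who stop medication are offered continued follow-up visits (4.4). With 10% loss from 80, power is back to about 81%. All of this stands, and is why the result is shown as a range. The plan does not state that reading, and its 10% in section 5.3 is scanner time for motion and technical loss, not attrition.
- **Missing data are covered.** Section 9.4.1 proposes selection and shared-parameter models and a weighted analysis. These address bias in the analysis; they do not supply an expected number of scan pairs.
- **The recruitment rate is only an intention.** The 160 might describe those treated, and Table 1 appears to mark 16 recruitment quarters (48 months × 4 = 192), although the table may have been damaged in extraction. Even so, the text does not reconcile with 200.
- **The d=0.38 is disclosed beside the power statement.** It is, but no power is attached to it, and the VS is a primary region under H1a.

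**Conclusion.** The concern holds. The contradictions between 70 and 80 per group at 81%, between 75% of 200 and 160, and among 140, 160 and 200 need no assumption about alpha or dropout. At one-sided 5% the 9.2 figure should be about 84% for 80 pairs, and 9.1 is within about 1.5 points of its claim.

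The effect on real power depends on what the sponsor meant. If 80 per group are injected and about 91% or more give usable pairs, 81% at d=0.42 is sound. With 25% loss (assumed), complete-pair power from 70 to 80 per group is 69% to 74% at d=0.42 and 61% to 66% at d=0.38. If PRE-only data also enter, it is about 71% to 79% and 64% to 72% (ρ from 0 to 0.5 assumed). For the VS effect the plan itself anticipates, power is 72% to 77% at 70 to 80 per group even with no loss. This should be fixed; it does not by itself invalidate the trial.

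**What to change.** Use one participant flow in sections 3.1, 3.2, 5.3, 9.1, 9.2 and 9.4.1: number recruited, number receiving injection 1, and expected number with both usable scans. Specifically:

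1. Correct either the 160 or the 75%, and reconcile 4 per month for 40 months with 200.
2. State alpha for the Group-by-Session test.
3. Define n as usable PRE/ON pairs, or state how PRE-only participants enter the GEE and the power calculation.
4. Restate power at that n for d=0.42 and d=0.38, over a stated range of day-55 scan retention.

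Suggested wording: *Of [N] recruited, [N] are expected to receive injection 1 and [n] per group to have usable PRE and ON scans; at one-sided alpha [x] this gives [ ]% power at d=0.42 and [ ]% at d=0.38.* The table of power by usable pairs above supplies the values if alpha is one-sided 5%.

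The cost is protocol and SAP wording only, with no extra patients. The stated power may rise or fall depending on which n and which retention the sponsor confirms.
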